1.1. Background

Obesity is a risk factor for the development of asthma (approximately 250,000 cases per year of asthma in the U.S. are related to obesity).¹ Obese patients often have poorly controlled asthma (with a nearly 5-fold risk of hospitalization compared with lean asthmatics) and do not respond as well to conventional controller therapy.²⁻⁶ Obesity particularly affects minority populations⁷: non-Hispanic blacks have the highest age-adjusted rates of obesity (47.8%) followed by Hispanics (42.5%), non-Hispanic whites (32.6%), and non-Hispanic Asians (10.8%). This is thought to account in part for the disparities of asthma in minority populations. There is a pressing public health need to develop interventions specifically for obese asthmatics.

One obvious intervention to consider for treatment of obese asthmatics is weight loss. Weight loss surgery significantly improves asthma-related outcomes.⁸⁻¹⁰ However, uncontrolled asthma increases surgical risk, and is an expensive, complex intervention only appropriate for a small subset of patients.^{11,12} Life-style interventions to promote weight loss in asthma may provide a simple, less expensive alternative, with the potential to reach a broader range of patients. Single center studies suggest that diet-induced weight loss might improve asthma,¹³⁻¹⁶ but there have been no large multicenter clinical trials addressing the efficacy of weight loss in patients with poorly controlled asthma.¹⁷

Our ultimate purpose is to test the hypothesis that weight loss through an intensive life style intervention will improve asthma control. But we first need to establish whether our weight loss intervention is effective in patients with asthma.

1.2. Primary objective

The primary objective of this study is to determine the effectiveness of an internet-based weight loss intervention in producing weight loss in obese patients with poorly controlled asthma.

1.3. Secondary objective

The ultimate purpose is to implement a multi-center weight loss intervention trial for obese patients with poorly controlled asthma.

1.4. Overview of study design

This will be a pilot study of a weight loss intervention at two centers, the University of Arizona and the University of Vermont. The primary outcome of interest will be the percent of participants achieving a 5% weight loss, which is the amount of weight loss that prior studies suggest is required to improve asthma control.

This will be a single arm-phase II futility trial; the “futility” to be assessed is the ability to produce weight loss. Such designs are widely used in efficiently informing decisions to proceed to Phase III clinical trials. This trial design is appropriate when the effect of the placebo arm can reasonably be estimated (weight loss is likely to be close to 0), and the toxicity of the treatment is minimal (no toxicity is anticipated related to weight loss).¹⁸ Therefore, this will be a single arm 6-month study of 40 participants (20 at each site). All participants will be assigned to the weight loss intervention, which is described in detail below.

2. Methods

2.1. Eligibility criteria

2.1.1. Inclusion criteria

- Physician diagnosis of asthma on regular controller therapy for at least the past 3 months
- Age: ≥ 18 years of age
- Obese: $\text{BMI} > 30 \text{ kg/m}^2$
- Poorly controlled asthma
 - Asthma Control Test Score $\leq 19^{19,20}$ or
 - use of rescue inhaler on average > 2 uses/week for preceding month, or
 - nocturnal asthma awakening on average 1 or more times / week in preceding month, or
 - ED/hospital visit or prednisone course for asthma in past six months
- Ability and willingness to provide informed consent
- Ability to access internet weight loss program for a trial period
- Completion of asthma, food and weight diary entries for same 3 consecutive days between visits 1 and 2

2.1.2. Exclusion criteria

- History of bariatric surgery
- Participant currently on weight loss drugs
- Any condition that puts the participant at risk from participation in a weight loss study or a condition that precludes participation in regular exercise as judged by the site physician
- Pregnancy (by patient self-report)
- Participation in another weight loss intervention within the last month
- Weight loss of ≥ 10 pounds in the last 6 months by self-report
- Intention to move out of area within the next 6 months

2.1.3. Rationale for eligibility criteria

Our goal is to enroll obese adults with asthma on asthma controller drugs. Enrollment criteria are purposely broad to ensure that the study population broadly reflects individuals who may be eligible for a weight loss intervention in a general medical setting. We are not excluding people who have co-morbid conditions or who smoke insofar as these individuals may benefit from the weight loss.

2.2. Asthma clinical assessments

Patients will undergo spirometry with post-bronchodilator reversibility testing at 0 weeks and 24 weeks, spirometry at all other visits will be done without bronchodilator administration. Questionnaires and diary entries will be available in English and Spanish.

- Asthma diaries on the PLAN website will be completed by participants throughout the study to record daily morning peak expiratory flow (PEF), daily asthma symptom scores, beta-agonist use, nocturnal asthma awakenings, and health care use. Diary data are used to identify episodes of poor asthma control and days with no asthma symptoms (asthma-free days).
- The Asthma Control Test (ACT) is a 4-week recall questionnaire that measures asthma control.¹⁹
- The Asthma Symptom Utility Index (ASUI) is a 2-week utility-weighted asthma symptom questionnaire.²¹
- The Marks Asthma Quality of Life Questionnaire (Marks AQLQ) assesses asthma specific quality of life.²²
- Medical Outcomes Study (SF36v1) is a measure of general health related quality of life which correlates with asthma outcomes.
- The IWQOL-lite is used to measure the effect of weight loss on QOL.²³
- Food Frequency,²⁴ activity²⁵ and motivation to lose weight²⁶, will be assessed using validated questionnaires.
- Anthropometrics will include height, weight, waist, hip circumference per NHANES III.
- For subjects who have not been seen in the pulmonary clinic in the last 12 months will have a brief physical exam at visit 2.
- Spirometry will be performed in accordance with ATS/ERS guidelines.²⁷
- Adverse effects will be assessed by open-ended questions at each visit and rated in severity.
- Interval health history will be recorded at each clinic visit. Records of all hospitalizations and, if necessary, deaths are obtained for verification of diagnoses and assessment of safety issues.
- Participants will be asked if they are pregnant at every visit, and if they become pregnant, they will be withdrawn from the study.
- Baseline questionnaires and exam will be administered to ascertain demographics including self-reported ethnicity and race, general health, co-morbid conditions, asthma symptoms, and medication use. Medical clearance for diet and moderate exercise will be provided by the study site physician.
- Exit questionnaires will be administered at the last visit to determine global assessments of treatment, adequacy of informed consent procedures, satisfaction with study procedures and personnel, and opinions about the intervention.
- Blood specimens will be collected for fasting blood glucose and analysis of metabolic and oxidative markers related to asthma. Excess blood specimens will be used for future asthma research with the patient's consent. Fasting blood draw may take place within 7 days of rest of the procedures scheduled for visit 2 or visit 6.

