2.3. Schedule of visits

Visit Number	V1	V2	N	-	P1 [†]	V3	V4	V5	V6
Time (week)		-2		0	2	6	12	18	24
Informed Consent	•								
Medical History	•	•				•	•	•	•
Interim Body Weight Measurement			•						
Orientation to weight loss program	•	•							
Start Weight Loss Program				•					
Provision of Chromebook computer		•							
Addressing website login issues and exercise strategies/concerns at home; facilitator contact					•				
Assessment of compliance with food, asthma and weight diaries		•							
Assessment of diary entry compliance		•				•	•	•	•
Spirometry	•	• [¥]				•	•	•	• [¥]
Asthma Control (ACT and ASUI)	•	•				•	•	•	•
Marks Asthma Quality of Life	•	•				•	•	•	•
Quality of Life (SF36v1)	•	•							•
Arizona Food Frequency Questionnaire	•								•
Stanford Brief Activity Questionnaire	•								•
Impact of Weight on Quality of Life	•								•
Motivation to lose weight (Tre-MORE)	•								
Height (V1 only), Weight, Hip and Waist Circumference	•	•				•	•	•	•
Blood draw (fasting)		•							•
End of Study Questionnaire									•

[†]The purpose of P1 is to check in the participant to make sure they have made contact with the weight loss facilitator, and are not having technical problems with the website, or with MyFitnessPal.

[¥]Spirometry at V2 and V6 will be pre and post bronchodilator, all other visits spirometry without bronchodilator.

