2.5.2. Sample size

The decision to proceed to the full scale trial will be based on a futility design analysis, which guided our sample size estimates. We will determine this study as futile if we cannot produce a clinically significant weight loss in a significant proportion of participants. A clinically significant weight loss is set at 5% (which is the amount of weight that appears to be necessary to improve asthma control based on previous studies, and also the amount of weight loss required for FDA approval of a weight loss medication). A significant proportion of the population is set at 35% (FDA recommend that a weight loss medication must produce a 5% weight loss in 35% of participants to be considered effective).³¹

A straightforward way to test for futility with a binary outcome is based on the binomial distribution³². For a given minimum sufficient efficacy (p_1) and level that would indicate the intervention was ineffective (p_0), the threshold for continuing, c , can be determined for any sample size, n , as follows: the largest value of c such that $P(X \geq c | p_0) \leq \alpha$, type I error, and $P(X \geq c | p_1) \geq 1-\beta$, power, i.e. minimize the type II error. Ineffective thresholds of 5% and 10% were considered (Table 2). To be conservative, drop-outs will count as weight loss failures. With 40 patients, we have 94% power and $\alpha < 0.001$ using a threshold of 9 and assuming $p_0 = 0.1$ vs $p_1 = 0.35$, i.e. if ≥ 9 individuals have clinically significant weight loss we would reject futility and continue on to a larger trial. For the 12 Hispanics, we would need ≥ 3 ($\alpha = 0.026$, $1-\beta = 0.87$) and ≥ 2 ($\alpha = 0.02$, $1-\beta = 0.85$) individuals to achieve 5% weight loss reject futility assuming $p_0 = 0.1$ vs $p_1 = 0.45$ and $p_0 = 0.05$ vs $p_1 = 0.35$, respectively.

Table 2: Power, type I error, and threshold for rejecting futility for a variety of futility, p_0 , and minimum efficacy, p_1 , thresholds

p_0	p_1	c	$N = 40$	p_0	p_1	c	$N = 12$
			$\alpha, 1-\beta$				$C, \alpha, 1-\beta$
0.1	0.25	6	0.013, 0.96	0.10	0.40	2	0.11, 0.92
		7	0.003, 0.90			3	0.026, 0.77
		8	< 0.001, 0.82			4	0.004, 0.56
	0.30	7	< 0.001, 0.94		0.45	2	0.11, 0.96
		8	< 0.001, 0.89			3	0.026, 0.87
		9	< 0.001, 0.80			4	0.004, 0.70
	0.35	9	< 0.001, 0.94	0.05	0.35	1	0.12, 0.96
		10	< 0.001, 0.88			2	0.020, 0.85
		11	< 0.001, 0.79			3	0.002, 0.65

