3.11. Stopping rules, interim analysis

Patients may withdraw from the study at any time.

There are no plans for interim outcome data analysis for this pilot study.

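### The exit questionnaire is scheduled only at V6, so the pilot's descriptive data on satisfaction, consent adequacy and opinions of the intervention will come from V6 attenders alone

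*Combined protocol and SAP*

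**What the plan says.** Section 2.2 states: "Exit questionnaires will be administered at the last visit to determine global assessments of treatment". The same item lists adequacy of the consent procedures, and then "satisfaction with study procedures and personnel, and opinions about the intervention".

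The schedule in section 2.3 has a row "End of Study Questionnaire" with a single mark, in the last column (V6, week 24). It has no early-termination column, and neither footnote concerns withdrawal.

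Leaving early is foreseen. Section 3.11 says "Patients may withdraw from the study at any time", and section 2.2 says of participants that "if they become pregnant, they will be withdrawn from the study".

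For the primary outcome, section 2.5.2 says "To be conservative, drop-outs will count as weight loss failures". That rule concerns weight loss. Section 2.5.3 plans descriptive statistics for all study parameters and is silent on missing exit questionnaires.

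**The concern.** The people who leave are those whose opinion of the program is most useful when the next trial is designed, and the plan describes no way of obtaining it. They lower the primary count as failures, yet they are absent from the only instrument described as asking what participants thought of the intervention.

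This is a pilot for a multi-center trial (sections 1.3 and 1.4). Section 2.5.1 says it will examine the practicality of data acquisition, the resources needed for contact and follow-up, and likely missing-data rates. If V6 attenders are more content than those who left, the exit data will make the program look more acceptable than it was to the enrolled group, and the reasons people gave up will not be recorded systematically. Consent adequacy is affected in the same way, since no other instrument is described for it. These views are hard to recover once the study has closed.

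**Working it through.** The plan states no figure on this point, so there is none to reproduce. The check has two parts.

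**1. Sections side by side**

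| Question | Where | What is found |
|---|---|---|
| When is the form given? | 2.2 | At the last visit |
| Which visit is that? | 2.3 | V6 only |
| Can people leave before V6? | 3.11; 2.2 | Yes, at any time; also withdrawn on pregnancy |
| Is there an exit visit or contact for leavers? | Whole document | None described |
| Is a reason for leaving recorded? | Whole document | None described |
| Is there a rule for missing exit forms? | 2.5.2, 2.5.3 | None; the drop-out rule covers the weight outcome |

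Other contacts that might fill the gap:

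- The P1 check at week 2 covers facilitator contact and technical problems (2.3, footnote).
- Missed chats prompt an e-mail, within an approach aimed at barriers to attendance (2.4.3).
- Site usage and lesson completion are logged (2.4.2), and all intervention contacts are documented (2.4.5).
- Food diaries are reviewed weekly (2.4.1). Asthma diaries and open-ended adverse-effect questions continue while the person takes part (2.2).

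These show that someone disengaged and give hints as to why. None is described as collecting satisfaction, opinions or a stated reason for leaving.

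**2. How far the missing forms could move a result (illustration only)**

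Inputs: N = 40 (section 1.4). The drop-out rate and the satisfaction proportion are assumptions, because the documents give neither.

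Let m be the number of drop-outs and s the number satisfied among the 40 − m attenders, taken as the whole number nearest to 80%. With nothing assumed about the drop-outs' views, the proportion satisfied among all 40 lies between s/40 (no drop-out satisfied) and (s + m)/40 (every drop-out satisfied).

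| Assumed drop-out | m | Observed at V6 | Lower bound | Upper bound |
|---|---|---|---|---|
| 10% | 4 | 29/36 = 0.81 | 29/40 = 0.725 | 33/40 = 0.825 |
| 20% | 8 | 26/32 = 0.81 | 26/40 = 0.65 | 34/40 = 0.85 |
| 30% | 12 | 22/28 = 0.79 | 22/40 = 0.55 | 34/40 = 0.85 |
| 40% | 16 | 19/24 = 0.79 | 19/40 = 0.475 | 35/40 = 0.875 |

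A directional scenario makes a further assumption: 90% of attenders and 30% to 50% of drop-outs are satisfied. V6-only collection would then report 90% in each case, while the all-participant figure would be:

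- 20% drop-out: (32 × 0.9 + 8 × 0.3)/40 = 0.78, or 0.82 with 0.5 in place of 0.3.
- 30% drop-out: (28 × 0.9 + 12 × 0.3)/40 = 0.72, or 0.78 with 0.5 in place of 0.3.

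The overstatement of 8 to 18 points follows entirely from the assumed gap in satisfaction.

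**The case against.** The strongest reply is that no objective or decision depends on this form. The primary objective is weight loss (1.2), acceptability is not a named objective or endpoint, and the go/no-go rule counts participants with 5% weight loss (2.5.2). Missing-data rates can be counted from attendance without asking drop-outs anything. All of this stands, and it limits the point to a descriptive instrument.

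Four stronger readings are tempting, and the documents do not support them.

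- *That the investigators could not tell people who left from people who stayed without losing weight.* Attendance and the weights scheduled at V3 to V6 separate these groups. What is missing is narrower: the leaver's own stated reason.
- *That nobody can ever know a visit is the last.* Pregnancy is asked about at every visit and leads to withdrawal, and a participant may announce withdrawal at a visit. In those cases the wording of 2.2 can be read to permit the form, although the schedule does not mark it. The clear gap is people who stop attending between visits.
- *That only program completers answer.* Someone who abandons the diet, chats or website but attends V6 still fills in the form.
- *That an upward bias of known size has been shown.* The direction is plausible, but the size is pure assumption. Sampling error is also wide: 29/32 has an exact 95% interval of about 75% to 98%, which covers the 78% to 82% of the 20% drop-out scenario. That does not remove the selection, because an interval computed on attenders makes no allowance for the views that are missing.

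**Conclusion.** The gap is real and modest. As written, satisfaction, consent-adequacy and opinion data come only from V6 attenders and may be selected, probably favourably. The amount cannot be stated. Under an assumed 20% drop-out with about 80% of attenders satisfied, the all-participant figure is bounded only by 0.65 and 0.85; at 30% drop-out, by 0.55 and 0.85.

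A reader might infer that the go/no-go decision is compromised. It is not: the count of participants with 5% weight loss makes no use of the questionnaire and has its own rule for drop-outs. The consequence is confined to what the pilot can say about why people leave and what they thought, where the other records are only indirect. The change is worth making because it is cheap and the information is hard to obtain later.

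**What to change.** In section 2.2 and as a footnote to the schedule in section 2.3, offer the existing End of Study Questionnaire plus one reason-for-leaving item at V6 or at withdrawal or recognised loss to follow-up, whichever comes first. Allow completion through the study website or by telephone, and say how loss to follow-up is recognised so that sites act at the same point.

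In section 2.5.3, state that results will be reported separately for V6 attenders and drop-outs, each with the number approached and the number responding. A pooled figure should not stand alone, because drop-outs who reply are themselves selected.

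Leave the primary rule that "drop-outs will count as weight loss failures" unchanged. It may be tempting also to invite withdrawn participants to V6 for a weight. That should not be part of this change: a withdrawn person with a measured 5% loss would then be ambiguous in the primary count.

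The cost is a footnote, one added item and one extra contact per drop-out, using a form and website that already exist. Some drop-outs will not respond, so selection is reduced and made visible but not removed.

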2.3. Schedule of visits

Visit Number	V1	V2	N	-	P1 [†]	V3	V4	V5	V6
Time (week)		-2		0	2	6	12	18	24
Informed Consent	•								
Medical History	•	•				•	•	•	•
Interim Body Weight Measurement			•						
Orientation to weight loss program	•	•							
Start Weight Loss Program				•					
Provision of Chromebook computer		•							
Addressing website login issues and exercise strategies/concerns at home; facilitator contact					•				
Assessment of compliance with food, asthma and weight diaries		•							
Assessment of diary entry compliance		•				•	•	•	•
Spirometry	•	• [¥]				•	•	•	• [¥]
Asthma Control (ACT and ASUI)	•	•				•	•	•	•
Marks Asthma Quality of Life	•	•				•	•	•	•
Quality of Life (SF36v1)	•	•							•
Arizona Food Frequency Questionnaire	•								•
Stanford Brief Activity Questionnaire	•								•
Impact of Weight on Quality of Life	•								•
Motivation to lose weight (Tre-MORE)	•								
Height (V1 only), Weight, Hip and Waist Circumference	•	•				•	•	•	•
Blood draw (fasting)		•							•
End of Study Questionnaire									•

[†]The purpose of P1 is to check in the participant to make sure they have made contact with the weight loss facilitator, and are not having technical problems with the website, or with MyFitnessPal.

[¥]Spirometry at V2 and V6 will be pre and post bronchodilator, all other visits spirometry without bronchodilator.

2.4. Weight loss intervention

The weight loss intervention will be implemented under the direction of [name] (Chair of Nutrition at UVM). Participants will be introduced to the weight loss program during visit 1. A research coordinator will show participants how to access the weight loss website, the MyFitnessPal program, and provide information to contact the assigned weight loss coach. The participant's picture will be taken to display on the chat page and on the biography page for their group when they use the study web site. Participants may opt out of this feature if they are uncomfortable having their picture displayed.

After visit 1, participants will be asked to enter information on the weight loss website and the MyFitnessPal program to display that they understand how to use the programs. Participants will have a 3-day trial period to enter daily asthma symptoms, food intake and exercise information online. The research team will assess completion of this trial period; only participants who enter complete diaries for same 3 consecutive days will be eligible to enroll in the study.

We will attempt to enroll participants into this study in groups of 5-10 to provide an adequate group for the weight loss intervention.

2.4.1. Basic components of the weight loss program

This 6-month intervention will include restricted calorie intake and increased physical activity. Key behavioral strategies to facilitate changes in dietary habits and activity patterns will be introduced, promoted and reinforced throughout the program. Weekly "group meetings" in a synchronous chat (i.e., in real time) led by a facilitator will be the venue for the group process. Extensive web-based resources to support behavior changes will be offered. The online groups will be "closed" such that those individuals who start the group remain in that group for the duration of their participation. Group chat sessions will meet online weekly for 6 months.

1. *Diet*

A balanced reduced calorie deficit diet will be prescribed. All participants will be given an individualized calorie goal. Emphasis will be placed on consuming a diet high in fruits, vegetables, and whole grains, and low in fat, sugar, salt and alcohol. Participants are asked to target fat intake to 25% of their overall calorie goal because a number of studies ^{28,29} suggest superior weight loss when fat and calories are both controlled.

Participants will record their daily calorie and fat intake daily electronically. They will have access on the study website to calorie and fat gram guides which use pull down menus and personally customized calorie/fat counters to facilitate ease of recording. The interventionist will review these diaries weekly and provide feedback to reinforce or shape new behaviors.

2. *Exercise*

Participants will be provided with graded goals to reach the recommended weekly minimum of 200 minutes of moderate intensity exercise by week 9 of the program. We will recommend brisk walking as in our previous studies. At visit 1, we will verify they have a safe place to exercise as in our previous studies, other forms of aerobic exercise will also be encouraged should the participant prefer. All exercise will be monitored using electronic diaries that include pull down menus for a wide range of activities.

3. *Behavioral strategies*

The major features of the behavior modification strategies in the program are based on Social Cognitive Theory³⁰ and are described below. [name] and [name] will be involved in training the bilingual lifestyle coach in cultural adaptation for Hispanic participants.

